We expect that the standard pulmonary TB treatment regimens recommended by the Union² can be optimized by using daily high dose rifampicin during Cat. 1 primo-treatment. For the here proposed pilot study, dosing of rifampicin would be doubled, while standard dose isoniazid, pyrazinamide and ethambutol would be maintained. Management decisions would be made after 2 weeks of intensive phase, based on remaining numbers and decline of TB bacilli on microscopy for AFB [auramine and fluorescein diacetate (FDA) vital staining]. Those with min. 1 log decline in the number of AFB by FDA smear, or already negative, would continue the unaltered regimen. Those not meeting these criteria would be referred for rapid DST by slide DST and/or Xpert MTB/RIF, depending on ease of referral. In case no rifampicin resistance is detected they would continue the optimized Cat. 1 treatment, with further monitoring by smear and rapid DST as per National TB Programme (NTP) indications, i.e. rapid DST in case a smear is positive at 3, 5 or 6 months; those diagnosed with rifampicin resistance at any time and by any technique would be switched immediately to the standard short "Bangladesh" MDR-TB treatment regimen. In the control arm, referral for rapid DST would be based on non-remittance of fever at the end of the second week, otherwise treatment management remains the same. Failures, relapses and other recurrences of the first-line regimen would all undergo rapid DST, and if not found to be rifampicin resistant they would be re-started on the same 6-month Cat. 1. The current Cat. 2 first-line retreatment regimen would no longer be used in the intervention arm.

Intervention and control treatment regimens (Rh: double dose rifampicin)

New cases	
- intervention:	2 HRhZE / 4 HRh
- control:	2 HRZE / 4 HR (Cat. 1 regimen)
Retreatment cases	
- intervention:	2 HRhZE / 4 HRh
- control:	2 SHRZE / 1HRZE / 5 HRE (Cat. 2 regimen)
MDR patients detected at any time	
	4 KHPtoGCEZ / 5 GCEZ (MDR regimen)

The expected benefits from this optimized treatment regimen cascade are:

1. Reduced occurrence of relapse with susceptible bacilli in patients with extensive disease, due to better sterilizing activity while maintaining the same treatment duration. Total absence of relapse with AFB smear at 2 weeks negative or scanty would suggest that shortening of the regimen to 4 months could be tried for fast converters.

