An interim analysis is thus planned at the time the last recruited patient finishes treatment, i.e. about 9 months after the end of recruitment. It will focus on assessment of drug toxicity versus suggested benefits of the intervention. This analysis will be primarily performed for the go/no-go decision and design considerations for the cluster-randomized trial. The decision on proceeding to the cluster randomized study will be based on the absence of excess toxicity, a trend toward a reduction of unfavourable outcomes (excluding relapse), and possible favourable effects on initially present low-resistance mutations / mutations acquired during treatment. It will also allow to adapt the design of the larger study particularly regarding the algorithm for resistance screening, and whether or not treatment shortening could be justified with rapid initial conversion.

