3.1 Primary endpoints

The primary efficacy endpoint is the incidence of adverse treatment outcomes. Following the WHO guidelines from 2010¹⁸, as currently in use in the NTP in Bangladesh, outcomes are defined as follows:

- Cured: A patient whose smear or culture was positive at the beginning of treatment but who was smear- or culture-negative in the last month of treatment and on at least one previous occasion.
- Completed: A patient who completed treatment but who does not have a negative sputum smear or culture result in the last month of treatment and on at least one previous occasion.

- Relapse: Cured previously from TB or completed treatment for TB and now having bacteriologically positive sputum for TB (at 12 months follow-up or at an earlier time point)
- Default: The patient whose treatment was interrupted for ≥ 2 consecutive months or more.
- Failure: Sputum positive for TB at 5 months or later during treatment. In line with current WHO recommendations, patients detected with MDR-TB or rifampicin resistance before this or another outcome applies and switched to the MDR-TB regimen will be excluded from the outcome analysis.¹⁸ Failure will also be declared if the regimen has to be changed for at least 2 drugs due to adverse events.
- Death: All-cause mortality between case registration and end of TB treatment (related or not to TB or TB treatment)
- Transfer out: A TB patient who transferred out to another recording and reporting unit and whose treatment outcome is unknown.

Analyses will be performed using the NTP smear-based recurrence (failure, relapse) definitions, but as a secondary approach culture-based definitions will be used.

Safety:

The primary safety endpoint will be the occurrence of any of the following:

- Serious Adverse Events
- Grade 3-4 Liver Toxicity following NIH common toxicity criteria (CTC), including transaminase increases to $>5-20$ ULN (grade 3), or > 20 ULN (grade 4)

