4.3 Sample size

The sample size selected is 1000 patients (500 randomized to intervention, 500 to control). The study will be conducted in eight DF Bangladesh outpatient clinics with an LED TB fluorescence microscopy laboratory that register about 2000 TB cases per year of which 65% are smear-positive pulmonary TB (new or retreatment). Enrolment will target 1000 randomised smear-positive pulmonary TB patients. Given an expected 5% refusal rate, it is expected that recruitment will require 9-10 months.

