Cured patients will be informed about the possibility and symptoms of relapse, the need to report if symptoms recur, and given an appointment for a follow-up check after 12 months. All patients still in the area (cured or defaulted) will have evaluation of clinical condition and sputum for AFB smear and TB culture once, 12 months after treatment was stopped, performing a home visit if required. Further follow-up for relapse will be passive.

Preservation of all smear-positive diagnostic- and recurrence sputa and referral for *rpoB* sequencing at ITM will continue for patients registered after study enrolment has stopped, to provide a better estimate for the prevalence of low-resistance mutations, and how these strains are affected by standard treatment. Additionally, the clinics will check reduction of bacillary load by auramine and FDA smears after 1 and 2 weeks also for these patients, not belonging to the study population and otherwise treated following routine programme guidelines, including normal dose rifampicin. This will provide further information needed for better understanding of the intervention benefits.

Sputum AFB smears will be performed at the 8 participating centres, which have already a long experience with auramine smears; continuous external quality assessment has been standard practice since many years.

The FDA technique will be introduced three months prior to the start of the study, and reliability will be assured before the results are used for the study.

Serum transaminase will be performed at the DF Bangladesh reference laboratory using a biochemistry automate and kits, according to Good Clinical Laboratory Practice.

All molecular bacteriology will be done at the accredited ITM Antwerp lab on forwarded ethanol-preserved specimens or strains. Primary culture will be performed at the DF Bangladesh Netrakona reference laboratory with continuous quality monitoring. All isolates found rifampicin-resistant on rapid DST (Xpert, slide DST), and all failure and relapse isolates, will be periodically sent to ITM lab for DST on LJ for confirmation, completion of resistance profile and strain identification in case of recurrence.

Serum transaminase

Only ALT will be performed for screening, as the more sensitive test; AST will be performed additionally in case a rise of ALT is found.

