2) Assessment of drug toxicity and initial treatment response will be performed at the time the last recruited patient finishes treatment. The data will be compiled at 9 months after the end of recruitment to ensure all treatment related data, including 8 months of treatment for retreatment cases in the control arm, are available. This analysis will be primarily performed for the go/no-go decision and design considerations for a possible next study, such as a cluster-randomized trial. The decision on proceeding to the cluster randomized study will be based on the absence of excess toxicity, a trend toward a reduction of unfavourable outcomes (excluding relapse), possible favourable effects overcoming low-resistance mutations.

3) A final analysis of the study endpoints, including relapse, will be performed one year after end of treatment of the last enrolled patients, i.e. about 2.5 years after enrolment start.

This analysis plan will be finalized and approved before database lock of the first interim analysis data. Major changes in statistical methodology used for the main and pre-planned analyses from this SAP, will require detailed description and justification in the statistical analysis report. The final analysis datasets, programs, and outputs are archived following good clinical practice guidelines (ICH E9).

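### The end-of-treatment interim is asked about treatment shortening before most of the intervention arm is due for its one active relapse check

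*Protocol*

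**What the plan says.** - **Use of the interim.** Protocol 2.1 places an interim about 9 months after recruitment ends. Its main purpose is the go/no-go decision on a cluster-randomized study. It is also meant to help adapt that study's design, including "whether or not treatment shortening could be justified with rapid initial conversion".
- **Relapse at that interim.** Among the go/no-go considerations, the same section lists "a trend toward a reduction of unfavourable outcomes (excluding relapse" in its closing bracket.
- **Signal for shortening.** This stands in Protocol 1.1, among the expected benefits: "Total absence of relapse with AFB smear at 2 weeks negative or scanty would suggest that shortening of the regimen to 4 months". The sentence ends by presenting the shorter course as something to attempt in fast converters.
- **How relapse is found.** Protocol 5.4 schedules "sputum for AFB smear and TB culture once, 12 months after treatment was stopped". Before that visit, cured patients are told of "the need to report if symptoms recur". Protocol 3.1 counts a relapse found before the 12-month visit.
- **Where relapse is analysed.** SAP 1: "A final analysis of the study endpoints, including relapse, will be performed one year after end of treatment of the last enrolled patients".
- **The same interim elsewhere.** Protocol 8 and SAP 1 describe it without mentioning shortening. SAP 1 keeps design considerations for a possible next study among its uses.
- **Recruitment.** Protocol 4.3: "it is expected that recruitment will require 9-10 months".
- **Analysis of converters.** Protocol 8.3.4 (objective 3) estimates relapse in patients with at least a one-log decline, or a negative or scanty smear, at week 2. SAP 7.3 estimates it, with a Wilson interval, only in those completely negative.

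**The concern.** The interim is given a question whose named evidence is mostly not yet collected. If the clause in Protocol 2.1 is acted on, the pilot's input on shortening would rest on week-2 smears, on-treatment outcomes and partial relapse information. The signal in 1.1 is also worded as total absence of relapse. Seeing no relapse when few patients have been checked would satisfy that wording while excluding very little.

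There is a second gap at the final analysis. The group that 1.1 names, negative or scanty, has no row of its own in SAP 7.3. Even the complete data, analysed as the SAP specifies, would not report relapse in that group.

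What is at stake is one element of the next study's design. A shorter regimen carried into a larger trial on thin evidence would put those later patients at risk of under-treatment.

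**Working it through.** **1. The plan's own recruitment figure.** Inputs from Protocol 4.3: 2000 registered cases a year, 65% smear-positive, 5% refusal, 1000 patients needed.

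2000 × 0.65 × 0.95 / 12 = 102.9 patients a month; 1000 / 102.9 = 9.7 months. This reproduces the stated 9-10 months.

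**2. When the relapse check falls.** New and retreatment patients in the intervention arm are all treated for 6 months (Protocol 2.1). The check is due at 6 + 12 = 18 months after enrolment.

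**3. Share due at the interim.** Let R be the months of recruitment. The interim is at month R + 9 from first enrolment. Only patients enrolled in the first R + 9 − 18 = R − 9 months are due. With even accrual (assumption), share = max(0, R − 9) / R.

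| R (months) | Interim at month | Share due | Of 500 | Months since treatment, whole arm |
|---|---|---|---|---|
| 9 | 18 | 0% | 0 | 3 to 12 |
| 9.72 | 18.7 | 7.4% | 37 | 3 to 12.7 |
| 10 | 19 | 10% | 50 | 3 to 13 |

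Patients not yet due have 3 to 12 months since treatment. The mean for the whole arm is R/2 + 3 = 7.5 to 8 months.

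**4. Sensitivity.**
- Uneven accrual at R = 10: the share is 0.1² = 1% if enrolment rises linearly from zero, and 1 − 0.9² = 19% if it falls linearly to zero.
- Interim exactly when the last 8-month control finishes (R + 8): the share is max(0, R − 10) / R, which is 0% for R = 9-10.
- Slower recruitment than planned (assumption): R = 12 gives 3/12 = 25%.

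**5. Due is not the same as known.** Protocol 5.4 incubates cultures for 8 weeks before calling them negative. At R = 10 the due patients reached their visit between months 18 and 19, so no negative culture from that visit would be final at the interim. Smears would be available, and the primary relapse definition is smear-based.

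**6. What zero relapses would show.** The Wilson 95% upper limit for 0 of n is 3.84 / (n + 3.84). For n = 50 it is 3.84 / 53.84 = 7.1%. If true relapse were 2% (illustration only), 50 checked patients would show none with probability 0.98⁵⁰ = 0.36. Converters would be only part of the 50, so their limit would be wider. These figures use actively checked patients only and give no credit for passive detection.

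**7. Groups side by side.** Protocol 1.1: negative or scanty. Protocol 8.3.4: at least one-log decline, or negative, or scanty. SAP 7.3: completely negative. The SAP group is the narrowest and drops the scanty patients that both protocol sections include.

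**The case against.** The strongest reply is that two tentative sentences have been joined into a conflict. Section 1.1 says absence of relapse would suggest that shortening could be tried. It is not a binding rule and is not tied to the interim. Section 2.1 does not adopt shortening or cite that signal. The operative statistical text (Protocol 8 and SAP 1) omits shortening, SAP 1 puts relapse in the final analysis, and SAP 7.3 already plans a Wilson interval. No tabulation of relapse by conversion is planned at the interim.

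Relapse information at that time is also not nil, because relapses reported before 12 months count. The 2% relapse in Protocol 8.4 is what the programme currently notifies, apparently without the 12-month check added for study patients. Comparing it with a limit based only on actively checked patients is not like for like.

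Much of this stands. It limits the point to one clause and to design input, and it means 2% should not serve as a pass mark. It is also true that relapse after 6 months of treatment cannot show what relapse would be after 4. Even the final analysis can only support trying a shorter regimen. The reply does not remove the clause. Section 2.1 still names shortening as a particular use of the interim, and the SAP does not withdraw it.

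A reader might also infer a share of 25% or more from slower recruitment. The documents plan 9-10 months. A longer recruitment period is an assumption, and it would ease the problem, not worsen it.

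**Conclusion.** The point holds as a minor one. At the planned recruitment pace, with even accrual and the interim 9 months after recruitment closes, the only active relapse check is due for 0 to 10% of the intervention arm (at most about 50 of 500). The remaining patients have 3 to about 12 months of passive detection. That is too incomplete to judge shortening by the signal the protocol itself names, although it is not an absence of information. Separately, SAP 7.3 does not report the negative-or-scanty group.

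A reader might infer that the interim or the go/no-go decision is unsound. The documents do not support that: relapse is expressly left out of the go/no-go outcomes and assigned to the final analysis. Nor do they show that shortening would be adopted at the interim. They say only that the interim may inform the next design.

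**What to change.** 1. In Protocol 2.1, limit the interim's input on shortening to describing the number of rapid converters and their on-treatment outcomes, marked as provisional. Place the judgement on shortening at the final analysis, after the 12-month visits.
2. At the final analysis, judge it on the upper limit of the Wilson interval already planned in SAP 7.3, not on zero observed relapses alone. No fixed threshold such as 2% is needed. The team can weigh the limit when designing the next study.
3. In SAP 7.3, add a row for patients negative or scanty at week 2, beside the completely negative group.

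The cost is one clause and one table row, using data already collected. The downside is timing. The interim falls at month 18-19 (9 or 10 + 9) and the final analysis at about month 30 (2.5 years). Shortening could therefore enter the next trial's design only provisionally for about 11-12 months, or be added later by amendment. The go/no-go decision, endpoints and conduct stay as they are.

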3. STUDY OBJECTIVES

Primary objective:

To compare a high-dose rifampicin standard TB regimen of 6 months duration with standard TB regimen with respect to adverse treatment outcome (relapse, failure, death and default) and toxicity, in TB cases (new or retreatment, pooled) not shown to have initial rifampicin resistance before one of the standard treatment outcomes applies.

Secondary objectives:

1. To assess whether the study regimen also cures low-level rifampicin resistant TB: by comparing and describing adverse treatment outcomes by initial rifampicin mutations (none, low-level, high)
2. To assess the effectiveness of FDA vital staining screening at two weeks of treatment for early switch of non-responding rifampicin resistant TB to MDR-TB treatment, versus clinical evaluation based on fever resolution. The proportions of rifampicin resistant cases started on MDR treatment within the first 2 months of primo-treatment as well as the proportion of initially present resistance never switched to the MDR regimen and not cured will be compared between the two arms.
3. To assess the negative predictive value of conversion at 2 weeks for relapse
4. To estimate the proportion of acquired rifampicin resistance among failures and relapses
5. To compare the predictive value of auramine with FDA staining at 2 weeks to predict unfavourable outcomes

3.1 Primary endpoints

The primary efficacy endpoint is the incidence of adverse treatment outcomes. Following the WHO guidelines from 2010¹⁸, as currently in use in the NTP in Bangladesh, outcomes are defined as follows:

- Cured: A patient whose smear or culture was positive at the beginning of treatment but who was smear- or culture-negative in the last month of treatment and on at least one previous occasion.
- Completed: A patient who completed treatment but who does not have a negative sputum smear or culture result in the last month of treatment and on at least one previous occasion.

- Relapse: Cured previously from TB or completed treatment for TB and now having bacteriologically positive sputum for TB (at 12 months follow-up or at an earlier time point)
- Default: The patient whose treatment was interrupted for ≥ 2 consecutive months or more.
- Failure: Sputum positive for TB at 5 months or later during treatment. In line with current WHO recommendations, patients detected with MDR-TB or rifampicin resistance before this or another outcome applies and switched to the MDR-TB regimen will be excluded from the outcome analysis.¹⁸ Failure will also be declared if the regimen has to be changed for at least 2 drugs due to adverse events.
- Death: All-cause mortality between case registration and end of TB treatment (related or not to TB or TB treatment)
- Transfer out: A TB patient who transferred out to another recording and reporting unit and whose treatment outcome is unknown.

Analyses will be performed using the NTP smear-based recurrence (failure, relapse) definitions, but as a secondary approach culture-based definitions will be used.

Safety:

The primary safety endpoint will be the occurrence of any of the following:

- Serious Adverse Events
- Grade 3-4 Liver Toxicity following NIH common toxicity criteria (CTC), including transaminase increases to $>5-20$ ULN (grade 3), or > 20 ULN (grade 4)

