 - Rifampicin sensitive:
 - Control arm: start Cat. 2
 - Intervention: re-start Cat. 1
 - Enquire, register adverse effects. Stop all drugs and refer in case of hepatitis suspicion (feeling sick, anorexia, vomiting, jaundice)
- Visit after 6 months (or 8 months for Cat. 2) V8: intervention + control arm
 - Clinical check, weight, temperature: signs and symptoms of TB absent?
 - Stop treatment, record attendance
 - Sputum smear for AFB: all patients
 - Declare cured if negative and inform about signs of relapse
 - Declare failure if positive and refer for rapid DST if AFB-positive

- Switch to MDR treatment if rifampicin resistant
- Rifampicin sensitive:
 - Control arm: re-register, start Cat. 2
 - Intervention: re-register, re-start Cat. 1
- Enquire, register adverse effects
- Make appointment for check-up after 12 months

- Visit 12 months after end of treatment V9 (intervention + control arm cured or defaulted)

- Reminders, home visit if not attending
- History from relatives / neighbours if not met (retreated or died of TB?)
- Clinical check: signs and symptoms of TB absent?
- If attending at the clinic only: weight, temperature
- Sputum smear and culture for AFB
 - If negative: further passive follow-up
 - If positive: declare relapse and refer for rapid DST
 - Switch to MDR treatment if rifampicin resistant
 - Rifampicin sensitive:
 - Control arm: re-register, start Cat. 2
 - Intervention: re-register, re-start Cat. 1

All enrolled patients will be monitored intensively for drug toxicity (clinical; liver enzymes during the first 2 months). Treatment will be interrupted in case of a serious adverse event, possibly due to the TB drugs, and patients referred to the nearest project hospital. In case of toxic hepatitis, after full recovery drugs will be re-introduced in hospital one by one, aiming at re-starting the same regimen since this toxicity is often transient and probably not rifampicin dose-related.

Unscheduled visits can take place at any time during the patients participation in the study. During these visits, all study procedures will be performed if needed, and data will be collected.

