7. SAFETY ASSESSMENT

7.1 Adverse events

Safety and tolerability of the treatments will be evaluated by recording Adverse Events (AE's) and grading laboratory and vital signs evaluations.

Definition of an Adverse Event

An Adverse Event (AE) is any untoward medical occurrence in a subject or clinical investigation subject administered a pharmaceutical product and that does not necessarily have a causal relationship with this treatment. An AE can therefore be any unfavourable and unintended sign (including an abnormal laboratory finding), symptom, or disease temporally associated with the use of a medicinal (investigational) product, whether or not related to the medicinal (investigational) product.

At each visit, the staff will ascertain the occurrence of any adverse events since the last visit. Once treatment has started and for its entire duration, clinic staff will enquire about the more common possible TB drug side effects: vomiting and anorexia, headache, tingling sensation in the extremities, insomnia, joint pain, rashes; in case streptomycin is administered also ringing in the ears, ataxia, hearing loss. Clinical examination for drug side effects will include checking the colour of the sclerae to detect jaundice (toxic hepatitis or hemolytic anemia); or joint swelling, muscle weakness etc. as

indicated by the reported symptoms. Patients will be referred to a Medical Officer or hospital in case of more severe symptoms or signs or for further investigations. In mild cases symptomatic treatment will be given.

Clinic staff will promptly record any AE on the patient file treatment follow-up sheet; for hospitalised patients this will be done by the Medical Officer on the hospitalization sheets. Liver test results will be systematically added to these documents.

In case of a SAE the clinic staff will refer the patient to the DF hospital; if jaundice is apparent or liver damage is suspected in any other way (including transaminase rise >5 ULN) all treatment will be stopped immediately and the patient referred for hospitalization. It is standard management to restart drugs one by one, and almost always there is no recurrence. In case of recurrence, these patients will not be withdrawn but one or more drugs need to be replaced. If 2 drugs are replaced, the outcome of treatment will be considered as adverse. This will be described in detail in the technical guide.

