#### 4.2. Efficacy study endpoints

##### *Primary endpoint*

The primary efficacy endpoint is the incidence of adverse treatment outcomes. Following the WHO guidelines from 2010, as currently in use in the NTP in Bangladesh, an adverse treatment outcome is defined as any occurrence of the following:

- Relapse: Cured previously from TB or completed treatment for TB and now having bacteriologically positive sputum for TB (at 12 months follow-up or at an earlier time point)
- Default: The patient whose treatment was interrupted for 2 consecutive months or more.

- Failure: Sputum positive for TB at 5 months or later during treatment. Failure will also be declared if the regimen has to be changed for at least 2 drugs due to adverse events.
- Death: All-cause mortality between case registration and end of TB treatment (related or not to TB or TB treatment)

Patients who are transferred out will be excluded from the outcome analysis.

In line with current WHO recommendations, patients detected with MDR-TB or rifampicin resistance before any outcome applies and switched to the MDR-TB regimen will be excluded from the outcome analysis.

Analyses will be performed using the NTP smear-based recurrence (failure, relapse) definitions, but as a secondary approach culture-based definitions will be used. In each analysis, if a patient has two events for the analysis of interest, the first endpoint will be taken into account, except for cured/completed followed by relapse which is considered as relapse.

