## **6. Analysis of main efficacy outcomes: adverse treatment outcome**

Counts and proportions (and 95% CI) of patients with any adverse treatment outcome, and by adverse treatment outcome category, will be presented. The confidence intervals for proportions will be estimated using Wilson's score method. Odds ratio's (ORs) of treatment effect on any adverse treatment outcome and 95% CIs for the OR will be estimated from a logistic regression model with effects for arm (intervention vs control), hospital, and stratum (new/re-treatment case). The p-value for the test of no difference among arms will be presented. If the number of events is low a logistic regression model with an effect for hospital may be used instead of the full model proposed.

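### Failure combines sputum-positive cases with drug changes for adverse events, so the Failure row and the acquired-resistance proportion are not purely bacteriological (minor)

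*Protocol*

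**What the plan says.** Protocol 3.1 and SAP 4.2 give failure two limbs. One is positive sputum at month 5 or later. The other is "Failure will also be declared if the regimen has to be changed for at least 2 drugs due to adverse events". Protocol 7.1 repeats the second limb when it describes suspected liver damage: "If 2 drugs are replaced, the outcome of treatment will be considered as adverse".

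Elsewhere the documents treat failure as bacteriological. The month 5 and end-of-treatment visits in Protocol 5.3 declare it on a positive smear, as does Protocol 5.4. Protocol 3.1 and SAP 4.2 call the main failure and relapse definitions smear-based and plan a culture-based version as a secondary approach.

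The primary objective (Protocol 3) compares the arms on "adverse treatment outcome (relapse, failure, death and default) and toxicity". The primary estimate is an odds ratio for any adverse outcome, and SAP 6 adds a breakdown: results overall "and by adverse treatment outcome category, will be presented". The categories are relapse, default, failure and death. For acquired resistance, Protocol 8.3.4 and SAP 7.4 divide by the failures and relapses that had no mutation at diagnosis. When a patient has two events the first one counts, except that relapse replaces an earlier cure or completion (Protocol 8.2, SAP 4.2).

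Neither document splits Failure by cause, plans an analysis without the adverse-event limb, or says whether that limb stays in the culture-based analysis.

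**The concern.** A reader of the category table will take Failure to mean that the regimen did not clear the bacilli. A patient whose sputum had cleared but who had two drugs replaced for toxicity sits in the same row. Under the first-event rule, that label also displaces any later bacteriological result.

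The acquired-resistance proportion has the same problem. A toxicity-driven case with no positive sputum can enter the denominator but can never supply a resistant isolate for the numerator, so it pulls the proportion down.

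The two limbs may also differ by arm for reasons unrelated to bacteriology. Replacing a second drug is an open-label decision. Retreatment controls receive a five-drug intensive phase and 8 months of treatment, against four drugs and 6 months in the intervention arm. Some of these episodes will also count in the primary safety endpoint, and nothing planned shows how many.

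**Working it through.** **Inputs.** All are from Protocol 8.4 unless stated: 500 per arm; unfavourable outcome 10% v 7%; failure about 2%, of which 50% culture-positive and about half of those rifampicin-resistant; clinically apparent hepatitis 1.5%, with an increase of 2 points considered. The documents give no rate for two-drug changes. I therefore take f, the share of hepatitis cases that end in such a change, as an assumption. I also assume that these patients have no other adverse outcome.

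**Plan's own figures.** For 10% v 7%, two-sided 5% and 80% power, the two-proportion formula gives 1356 per arm. With the continuity correction it gives (1356/4) × [1 + √(1 + 4/(1356 × 0.03))]² ≈ 1422, against 1421 stated. The stated hepatitis p of 0.047 is matched by 8 v 18 of 500 (uncorrected chi-square, 0.0469).

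**Composite.** Control = 10 + 1.5f and intervention = 7 + 3.5f (percent), so the benefit is 3 − 2f points.

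| f | Control % | Intervention % | Benefit (points) | OR | Power at 500 per arm |
|---|---|---|---|---|---|
| 0 | 10.0 | 7.0 | 3.0 | 0.68 | 39.8% |
| 5% | 10.075 | 7.175 | 2.9 | 0.69 | 37.2% |
| 10% | 10.15 | 7.35 | 2.8 | 0.70 | 34.7% |
| 25% | 10.375 | 7.875 | 2.5 | 0.74 | 27.8% |
| 50% | 10.75 | 8.75 | 2.0 | 0.80 | 18.6% |
| 100% | 11.5 | 10.5 | 1.0 | 0.90 | 7.3% |

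The benefit shrinks but keeps its sign even at f = 100%. Cancelling it needs a net excess of 3 points, which is 15 of 500.

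**Failure row.** The expected fall is 2% × 0.5 × 0.5 = 0.5 points (2.5 of 500), from 2.0% to 1.5%. With the adverse-event limb, control = 2 + 1.5f and intervention = 1.5 + 3.5f:

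| f | Control % | Intervention % | Intervention minus control (points) |
|---|---|---|---|
| 5% | 2.075 | 1.675 | −0.4 |
| 10% | 2.15 | 1.85 | −0.3 |
| 25% | 2.375 | 2.375 | 0 |
| 50% | 2.75 | 3.25 | +0.5 |

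A net excess of 3 patients (0.6 points) reverses the fall. Against a 2-point hepatitis excess (10 of 500), that corresponds to f = 30%.

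**Sampling error of that row.** SE = √(0.02 × 0.98/500 + 0.015 × 0.985/500) = 0.83 points, so the 95% interval is about ±1.6 points around a 0.5-point difference.

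**Resistance denominator.** At programme rates, 2% failure plus 2% relapse is about 20 of 500, before removing patients with a mutation at diagnosis. Three added toxicity-driven cases multiply the proportion by 20/23 = 0.87. A smaller starting denominator is diluted more.

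**The case against.** The case for leaving the rule alone is strong on the primary analysis. The endpoint is a declared composite that already contains default and deaths from any cause, so it was never a measure of bacteriological failure. Protocol 7.1 says: "It is standard management to restart drugs one by one, and almost always there is no recurrence". Replacement is considered only after recurrence, and the rule then needs two drugs, so f is probably well below 10%. The 2-point hepatitis excess is a detectability threshold in Protocol 8.4, not an expectation, and Protocol 1.2 reports no increase in liver toxicity in the studies it cites. The 0.5-point failure signal cannot be read at this sample size with or without the rule. Protocol 8.4 also credits it to early resistance detection as well as to the dose. Protocol 8.3.5 and SAP 6.1 look at new and retreatment cases separately, which partly addresses the regimen difference. All of this stands, and it limits the point to reporting. It does not answer the mislabelled row or the denominator.

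A reader might infer more than the documents support:

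- **That toxicity could reverse the primary result.** On the protocol's own figures it cannot (table above).
- **That toxicity is always counted twice.** Overlap arises only when the event is a serious adverse event or grade 3-4 liver toxicity. That is likely for hepatitis, because suspected liver damage leads to hospital referral. A non-serious event below that grade counts only in efficacy.
- **That the interim sets toxicity against a benefit that already contains it.** Protocol 2.1 says "It will focus on assessment of drug toxicity versus suggested benefits of the intervention", but the go/no-go criteria in the same section list excess toxicity and unfavourable outcomes separately.
- **That toxicity interruptions inflate Default.** Protocol 5.3 says "Treatment will be interrupted in case of a serious adverse event, possibly due to the TB drugs", and default is defined without regard to cause, but nothing suggests that such interruptions last two months.
- **That the 2% planning rate excludes adverse-event changes.** The documents do not show this either way.

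**Conclusion.** The point holds as a minor one. The Failure row cannot be read as bacteriological failure, and the acquired-resistance proportion is diluted by any toxicity-driven case without a positive sputum. The composite odds ratio is at most diluted, by 2f points: 0.1 at f = 5%, 0.2 at f = 10%, 1.0 at f = 50%.

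These sizes rest on the assumed f, on hepatitis at 1.5% v 3.5%, and on hepatitis being the only trigger. With no excess toxicity there is no net shift from this source in new cases. The direction is not fixed: Protocol 1.1 describes the control retreatment regimen as more toxic, so changes there would flatter the intervention. An unsplit row cannot show which way the effect runs, and that is the reason to split it.

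**What to change.** Leave the composite as defined, and make five changes in the SAP:

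1. **SAP 4.2 and 6:** report regimen changes of at least two drugs for adverse events by arm, as a category separate from sputum-positive Failure.
2. **SAP 7.4:** restrict the denominator to sputum-positive failures and relapses without a mutation at diagnosis.
3. **SAP 4.2:** state that the culture-based secondary analysis counts only bacteriological failure.
4. **SAP 6:** add one sensitivity logistic model in which an adverse-event-driven change alone is not counted as adverse. Show it beside the composite at the end-of-treatment interim and the final analysis.
5. **SAP 8.2:** tabulate by arm how many of these patients also meet the primary safety endpoint.

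The cost is one extra row, one extra model and a small cross-table. No new attribution is needed, because applying the rule already requires someone to decide that the change was due to adverse events. That decision remains open-label, which limits the sensitivity model. The SAP should also say how the model treats these patients if they have no 12-month sputum. Protocol 5.3 describes that visit for cured or defaulted patients, and SAP 4.1.1 would otherwise return them as adverse. Neither the Default definition nor the interim's benefit measure needs to change, and no clinical rule is affected.
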